These six life tasks reflect two underlying constructs: Activity limitations and Participation deficits. The WHO-DAS 2.0 is based off of the International Classification of Functioning, Disability and Health (ICIDH-2), which categorizes disability into three categories: physiological, activities and participation. The WHO-DAS 2.0 has been translated into 15 languages and tested in 13 countries. The six domains have a factor loading of 0.82 to 0.98 and all load onto the general disability factor. Participants will be asked to complete this at all time points. We will use the WHO-DAS 2.0 screener which is a 12 item measure at screening. The WHO-DAS 2.0 screener explains 86% of the variance in the full measure and will reduce burden at screening. As the WHO-DAS is the primary outcome measure, we will use the full, and more valid, 36 item measure during the study.

3. Columbia-Suicide Severity Rating Scale (C-SSRS): The C-SSRS is the gold standard for suicide assessment. It is used by the VAs Center of Excellence for Suicide Prevention. The C-SSRS was developed by Columbia University and is used extensively across primary care, clinical practice, surveillance, research, and institutional settings. The C-SSRS in one study showed 100% sensitivity and specificity in identifying individuals who attempted suicide. Across three major randomized controlled trials, the C-SSRS demonstrated convergent, divergent, and predictive validity; sensitivity to change; sensitivity and specificity of the instrument; and internal consistency of the intensity subscale. (Posner et al., 2011) is part of a national and international public health initiative involving the assessment of suicidality, including general medical and psychiatric emergency departments, behavioral health organizations, medical homes, community mental health agencies, primary care, clergy, hospices, schools, college campuses, US Army, National Guard, VAs, Navy and Air Force settings, frontline responders, substance abuse treatment centers, prisons, juvenile justice systems, and judges to reduce unnecessary hospitalizations. At the screening and 12th session visit, this questionnaire will be administered by a member of the research staff.

b. Questionnaires

The questionnaires described by construct below will be administered at certain time points. Questionnaires may be administered in person at baseline and after the 12th session.

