Questionnaires will be mailed or administered via phone after the 4th sessions, as well as 6 months post-treatment.

1. Case Definition of GWV Illness (GWI) – Kansas Case Definition (described above).
2. The Fatigue Severity Scale (FSS): The FSS is designed to differentiate fatigue from clinical depression, since both share some of the same symptoms (Takasaki & Treleaven, 2013). The FSS consists of a short questionnaire that requires the participant to rate his or her own level of fatigue. This measure has demonstrated good reliability, with a higher Cronbach's alpha indicated for the newer severity scale, as well as a correlation of 0.976 between the initial and current Fatigue Severity scales for a sample of 235 participants in seven groups. The FSS will be used to capture fatigue as a secondary outcome.
3. Pain Disability Index (PDI) & Pain Inventory (MPI): We will assess pain with 10 questions from two measures. We will first include the 7 item Pain Disability Index that assesses disability from pain. This measure has been found to be valid, have adequate test-retest reliability and be responsive to change in clinical trials (Soer et al., 2012; Tait et al., 1990). We will also use the 3 item West Haven Yale Pain Inventory that measures pain severity which has excellent test-retest reliability (0.74), internal consistency (.80), criterion validity, construct validity (Kerns et al., 1985). Both of these are commonly used together to characterize the suffering associated with pain.
4. Patient Health Questionnaire (PHQ-15): The PHQ is a self-administered questionnaire yielding algorithmic diagnoses of psychiatric illness. We will give the somatic symptoms (15 items) module. Patients are instructed to code each symptom based on whether it bothered them over the preceding 2 weeks: "not at all", "several days", "more than half the days"; or "nearly every day". The PHQ-15 was validated on a sample of 6,000 and found to be reliable, valid and responsive to change (Kroenke et al., 2002).

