Data analyses will be conducted both on-site by study investigators and with proper approvals, including DUAs, at our affiliate institutes by current and future study investigators. All analyses will be primarily performed on an intention-to-treat basis. The statistical significance will be defined by a p value < 0.05 , unless specified otherwise. Calculations of the means, standard deviations, proportions, histograms, etc., will be conducted to explore the distributions of the data, identify outliers, and calculate correlations between variables. We will also determine confounders that need to be controlled for in our analyses. We will particularly examine if we need to control for depression measured with the PHQ-8 or PTSD symptoms measured with the PCL based characteristics that exhibit differences at the baseline (pre-intervention).

Due to repeated measures, we will analyze the data using mixed model analysis, with participants nested within therapists modeled by random effects. To address H1, disability (WHODAS II scores) will be treated as the dependent variable, and treatment assignment [PST vs. Health education], time [pre- vs. post-intervention] and their interaction will be modeled as fixed effects. Differences in the improvement of disability between Problem-solving therapy and Health education will be evaluated by the treatment by time interaction. Linear contrasts will be constructed to evaluate the improvement in disability for each treatment separately. Variables such as age, gender, education and the confounders identified in the preliminary analysis will be controlled as covariates in the statistical analyses. Data transformations (e.g., square root, log,

etc.) will be used to normalize data where necessary. The same mixed model analysis strategy will be applied to address H2a, H2b, H3a and H3b. We will also explore, using this same mixed model strategy, the impact of PST therapy on each of the four individual neuropsychological tests scored as a composite and scored individually (Category Test, CPT 3, Stroop Test, and TMT). We will use the same data analysis strategy to examine all secondary outcomes. These will be reported as secondary outcomes and will primarily be used to generate hypotheses.

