- van der Zee, C. H., Priesterbach, A. R., van der, D. L., Kap, A., Schepers, V. P., Visser-Meily, J. M. et al. (2010). Reproducibility of three self-report participation measures: The ICF Measure of Participation and Activities Screener, the Participation Scale, and the Utrecht Scale for Evaluation of Rehabilitation-Participation. *J.Rehabil.Med.*, 42, 752-757.
- Ware, J., Jr., Kosinski, M., & Keller, S. D. (1996). A 12-Item Short-Form Health Survey: construction of scales and preliminary tests of reliability and validity. *Med.Care*, 34, 220-233.

Summary List of Measures and Timeline

Domain	Study Instruments	# of Items	Screening	Baseline	4 week	12 week	24 week (6 month)
Screening	General Screening Questionnaire	27	X				
	Columbia Suicide Severity Rating Scale [C-SSRS]	26	X			X	
	Mini International Neuropsychiatric Interview [MINI]	23	X				
	World Health Organization Disability Assessment Schedule- 12 items [WHO-DAS]	12	X				
Estimated Completion Time for Screening Domain: 35-45 minutes							
Problem-Solving	Problem Solving Inventory [PSI]	32		X	X	X	X
	Behavioral Responses to Illness Questionnaire [BRIQ]	19		X	X	X	X
Estimated Completion Time for Problem-Solving Domain: 9 minutes							
Gulf War Illness	Fatigue Severity Scale [FSS]	9		X		X	X
	KANSAS Questionnaire [KANSAS]	29	X			X	
	Patient Health Questionnaire 15-items [PHQ-15]	15		X	X	X	X
	Pain Disability Inventory [PDI] & Pain Inventory [MPI]	10		X		X	X
	MOS Sleep Scale [MOS-Sleep] & Insomnia Severity Index [ISI]	19		X		X	
Estimated Completion Time for Gulf War Illness Domain: 16 minutes							
Disability	World Health Organization Disability Assessment Schedule- 36 items [WHO-DAS]	36		X	X	X	X
	Veterans RAND 12 Item Health Survey [VR-12]	12		X		X	
	USER-P (activity satisfaction and frequency) [USER-P]	21		X		X	X
	MOS Social Support [MOS-SS]	8		X		X	X
Estimated Completion Time for Disability Domain: 14 minutes							
Participant Characterization	Alcohol Use Disorders Identification Test Alcohol Consumption Questions [AUDIT-C]	4		X		X	
	Post Traumatic Stress Disorder Checklist [PCL-5]	20		X		X	X
	Patient Health Questionnaire 8 items [PHQ-8]	9		X		X	X
	Brief Traumatic Brain Injury [BTBIS]	4		X			
	Demographics [Demo]	30		X		X	X
	Healthcare Access [HCA]	17		X		X	X
Estimated Completion Time for Characterization Domain: 12 minutes							
Veterans Perceptions of Problem-Solving and Health Education	Working Alliance Inventory (Self) [WAI]	12			X	X	
	Target Complaints Questionnaire [GOALS]	6		X		X	

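### The H1 model has a two-level pre/post time factor although the 36-item WHO-DAS is collected at four visits: week-4 scores do not enter the primary analysis, and the 6-month scores have no specified contrast

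*Combined protocol and SAP*

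**What the plan says.** **Collection.** The WHO-DAS 2.0 entry under Assessment Instruments (Screening, item 2) says "Participants will be asked to complete this at all time points", and adds: "As the WHO-DAS is the primary outcome measure, we will use the full, and more valid, 36 item measure during the study". In the Summary List of Measures and Timeline, the row "World Health Organization Disability Assessment Schedule- 36 items [WHO-DAS" is marked at baseline, 4 weeks, 12 weeks and 24 weeks (6 months). Table 2 shows the same four questionnaire points. The Questionnaires section confirms the two remote ones: "Questionnaires will be mailed or administered via phone after the 4th sessions, as well as 6 months post-treatment".

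**Analysis.** Data Analysis, part a, says: "Due to repeated measures, we will analyze the data using mixed model analysis, with participants nested within therapists modeled by random effects". For H1, treatment assignment and "time [pre- vs. post-intervention] and their interaction will be modeled as fixed effects", and the difference in improvement "will be evaluated by the treatment by time interaction". The linear contrasts mentioned there are for improvement within each arm. Secondary outcomes follow the same strategy. A general sentence on other outcomes of interest names no visit.

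**Missing data.** The only governing statement is "All analyses will be primarily performed on an intention-to-treat basis". Under Participant Compensation, a participant who stops may attend an exit assessment. The plan does not say whether that assessment serves as the post-intervention score.

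**The concern.** A two-level time factor cannot hold four visits. Week 4 falls within the 12-session treatment, so it is neither pre nor post, and its scores have no place in the written model. For someone who answers at week 4 and is not assessed again, the primary analysis then uses baseline alone. A likelihood analysis of two visits is valid only if missingness at week 12 is unrelated to the outcome once baseline, arm and covariates are taken into account. Early response is a plausible reason to leave a talking therapy, and the trial will have measured it.

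The 6-month scores raise a separate gap. They are collected and participants are paid for them, yet no hypothesis, model level or contrast is assigned to them. Whether any benefit lasts has no stated analysis.

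**Working it through.** **1. Visits against model.**

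| WHO-DAS visit | Place in the written H1 model |
|---|---|
| Baseline | pre |
| Week 4 | none |
| Week 12 | post, on the natural reading |
| 6 months | no named level or contrast |

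Two of the four scheduled visits have no explicit place. The plan gives no power, SD, correlation or dropout figure, so there is nothing to reproduce. The sizes below rest on assumed inputs.

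**2. Precision.** Assume n = 150 per arm (half of the maximum of 300), SD 1, correlation r of baseline with later visits, a fraction d lost between weeks 4 and 12, and no therapist clustering. Let R be the residual variance of the week-12 score given the earlier visits in the model. The variance of the treatment by (week 12 minus baseline) contrast is

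V = (2/n) × [2(1 − r) + R·d/(1 − d)].

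Take all correlations at 0.7 and d = 0.2:
- Baseline only: R = 1 − 0.49 = 0.51. V = (2/150) × (0.6 + 0.51 × 0.25) = 0.00970, SE 0.0985.
- Baseline and week 4: R = 1 − 0.98/1.7 = 0.4235. V = (2/150) × (0.6 + 0.4235 × 0.25) = 0.00941, SE 0.0970.
- Variance reduction: 1 − 0.00941/0.00970 = 3.0%.

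If the week 4 to week 12 correlation is 0.8 instead, R = 0.3216 and the reduction is 6.5%. Over correlations 0.5-0.9 and d from 10% to 30%, it runs from 0.9% to 14.5%.

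**3. Bias, dropout rising smoothly with the week-4 score.** Large-sample simulation (1,000,000 per arm). The true effect is −0.20 SD at week 4 and −0.40 SD at week 12, with negative values favouring PST. The log-odds of dropout rise by 1 per SD of week-4 score where stated. The correlation pairs (baseline with later visits; week 4 with week 12) are 0.5/0.6, 0.7/0.7 and 0.7/0.8.

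| Dropout depends on week 4 in | Dropout | Two-visit estimate (range) |
|---|---|---|
| both arms equally | 10-30% | −0.397 to −0.403 |
| PST only | 10% | −0.421 to −0.433 |
| PST only | 30% | −0.456 to −0.493 |
| control only | 10% | −0.367 to −0.380 |
| control only | 30% | −0.309 to −0.343 |

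The model that includes week 4 gives −0.396 to −0.403 throughout. One-arm bias is therefore about 0.02-0.09 SD, and its sign depends on the arm.

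**4. Bias, dropout split at the predicted week-4 score.** True effect −0.35 SD, correlations 0.6 and 0.75. Percentages are dropout if week 4 is worse / better than predicted from baseline.

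| PST | Control | Two-visit estimate | Bias |
|---|---|---|---|
| 35% / 10% | flat 20% | −0.41 | −0.06 |
| 25% / 15% | flat 20% | −0.37 to −0.38 | −0.02 to −0.03 |
| 35% / 10% | 27% / 13% | −0.37 to −0.38 | −0.02 to −0.03 |
| 35% / 10% | 35% / 10% | −0.35 | 0 |
| 10% / 35% | flat 20% | −0.29 | +0.06 |
| 35% / 10%, half of dropouts in each arm still assessed | flat 20% | −0.38 | −0.03 |

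With week 4 in the model, each estimate is −0.35. With no true effect, the first row gives −0.06. From the formula in step 2 with r = 0.6 and d = 0.2, the SE is √[(2/150) × (0.8 + 0.64 × 0.25)] = 0.113. A shift of 0.06/0.113 = 0.53 SE raises a two-sided 5% error rate to about 8%.

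**The case against.** **The bias depends on an assumed mechanism.** The documents contain nothing on who drops out or why. If early response drives dropout equally in both arms, the two-visit model is essentially unbiased. A reader might infer that the primary estimate will be inflated, by 18% for example (0.06/0.35 is about 0.17 from the rounded figures). That is one row of the table; the opposite row biases toward the null. This objection stands, and only a range can be claimed.

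**Leaving therapy is not the same as missing the outcome.** Participants who stop may attend a paid exit assessment, week-12 questionnaires may be completed by mail or phone, and the protocol promises a concerted effort to reach participants. This also stands: assessing half of the dropouts roughly halves the bias. But the exit visit is optional, and the plan does not say whether it counts as the post score.

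**Week 12 is the natural meaning of post.** A reader might infer that the primary endpoint is open between week 12 and 6 months. The documents do not support that. Baseline is called pre-intervention, the later visit is described as a follow-up after treatment, and the same model serves H2b, whose neuropsychological tests exist only at baseline and week 12. What is missing is the explicit label.

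**A pre/post contrast is legitimate, and H1 does not ask about durability.** Both are true. A week-12 contrast from an all-visit model answers the same H1 question under a weaker missing-data assumption. Nor do the documents say that the 6-month data will go unanalysed: the general sentences could be stretched to cover them, but they specify no model or contrast.

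**Conclusion.** The gap is real and of moderate weight. Four visits are collected, the H1 model uses two, and nothing else in the plan assigns the week-4 or 6-month WHO-DAS scores. As written, the analysis makes a stronger missing-data assumption than the collected data require.

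On assumed inputs, the possible bias runs from zero to about 0.06-0.09 SD, direction unknown. It is near zero when the dropout mechanism is the same in both arms, and it shrinks as more dropouts are assessed. The precision gain alone would hardly justify the change: about 1-15% in variance, and 3-6.5% at 20% dropout with a baseline correlation of 0.7. The case rests on protection against differential dropout and on having a prespecified durability contrast. None of these sizes is predicted by the documents.

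**What to change.** - Fit one mixed model with time as a categorical factor over baseline, week 4, week 12 and 6 months, with an unstructured within-person covariance. Keep the therapist random effect.
- Name the treatment-by-time contrast at week 12 (change from baseline) as the test of H1. With four levels the overall interaction has three degrees of freedom, so citing the interaction alone would no longer identify the test.
- Report the 6-month contrast as a secondary durability result.
- State whether an exit assessment counts as week 12, and state the missing-data assumption.
- Do the same for the PSI (H2a), which is also scheduled at all four visits.
- Before defining the last level, reconcile the visit's timing. Participant Compensation, the section on the 4th week and 6th month assessment, and Questionnaires place it six months after treatment; the Summary List labels it 24 weeks (6 months). If both count from the start of a 12-week treatment, these are roughly week 38 (12 + 26) and week 24.

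The cost is SAP wording and a few more covariance parameters: 4 × 5/2 = 10 for four visits against 2 × 3/2 = 3 for two. No new data are needed.

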Participants will be given or mailed a Health Education workbook after the baseline assessment. For participants enrolled at the Bedford VA and Canandaigua VA, the Study Coordinator from the East Orange VA may mail the Health Education workbook. The Health Education workbook will be used in conjunction with the sessions. The content in the Health Education workbook includes didactic information on a variety of health topics pertinent to GWVs, i.e., pain, improving cognition, sleep, diet and physical activity. This information will also be reviewed with the Study Provider during each session. Similar to those randomized to the PST group, at the Study Provider's or PI's discretion, the Health Education protocol may vary in order to meet a Veteran's needs (e.g., changing the order of the information given, having an additional session if feasible).

Participants who are assigned to the health education control condition may be offered the 12-session PST program at the end of the study.

During the sessions, participants will regularly be asked questions on their perception of the sessions, treatment and if they have any new health concerns.

Reducing Attrition

To reduce attrition and the burden on the Veteran, all therapy sessions are done over the phone or video to phone if available. In addition, we plan to make phone calls to remind participants about their scheduled appointments (similar to the VA's automated appointment reminder system). PST has been successfully implemented over the telephone. Prior to starting the treatment, the participant and Study Provider may determine the time that is best for the Veteran (including nights and weekends) and may determine ground rules (for example, not having anyone else in the room, shutting off other telephones to remove distractions). The Study Provider and Veteran may also establish verbal signals to substitute for non-verbal cues, for example, "that's great" or "can I interrupt."

Participants will be allowed to begin or continue with their existing medical regimen throughout the course of the trial and make changes to their existing treatments. Adherence to medical protocols and participation in alternate treatments will be evaluated by a questionnaire at the assessments and this will be controlled for in analyses. The Study Provider may make additional recommendations for additional health care if needed or as appropriate.

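### With complete data the H1 interaction equals the unadjusted difference in mean change; adjusting for baseline WHO-DAS would gain precision and deal with chance baseline imbalance

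*Combined protocol and SAP*

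**What the plan says.** The Data Analysis section (a. Data) specifies a "mixed model analysis, with participants nested within therapists modeled by random effects". For H1 the response is the WHO-DAS score at each time, baseline included. The fixed part of the model is given as: "treatment assignment [PST vs. Health education], time [pre- vs. post-intervention] and their interaction will be modeled as fixed effects". The test is stated as: "Differences in the improvement of disability between Problem-solving therapy and Health education will be evaluated by the treatment by time interaction". Separate linear contrasts give the improvement within each arm.

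On covariates the section says: "Variables such as age, gender, education and the confounders identified in the preliminary analysis will be controlled as covariates in the statistical analyses". It singles out PHQ-8 and PCL as candidates, to be judged by whether they differ at baseline. Baseline WHO-DAS is not named as a covariate, and no covariate-by-time term is mentioned. The Reducing Attrition section adds adherence to medical protocols and other treatment: "participation in alternate treatments will be evaluated by a questionnaire at the assessments and this will be controlled for in analyses".

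Analyses are primarily by intention to treat, and the same model serves H2a, H2b, H3a and H3b. The document gives no covariance structure, missing-data method, power calculation or pre-post correlation. The Summary List of Measures and Timeline schedules the 36-item WHO-DAS at baseline and at 12 weeks.

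**The concern.** In the model as written, the baseline score is a response, and each arm has its own baseline mean. The interaction then subtracts the whole baseline difference between arms. Regression on baseline would subtract only the part that predicts follow-up. Three things are at stake.

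- **Precision.** Unless the pre-post correlation is very high, change scores carry more noise than baseline-adjusted follow-up scores.
- **Chance imbalance.** If the arms happen to differ on baseline WHO-DAS, regression to the mean enters the H1 estimate.
- **What adjustment means.** The plan says that age, gender, education and identified confounders are controlled. If they enter as baseline main effects, the usual reading of such a sentence, the complete-data H1 estimate is the same with or without them. A reader of the results could believe otherwise.

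**Working it through.** The plan has no power figure to reproduce.

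**Inputs from the document:** two time levels, the three fixed effects, the interaction test, a sample of up to 300, and the 0.05 level ("The statistical significance will be defined by a p value < 0.05").

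**Assumptions, not in the document:** 300 analysed, 1:1 allocation, two-sided test, equal SDs at both times, no therapist clustering, an effect of 0.30 SD, and rho (pre-post correlation) of 0.3, 0.5 or 0.7.

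**1. Identity.** Let T be the arm and X a time-constant covariate with a main effect only. Write Y0 = a + bT + gX + e0 and Y1 = a + bT + c + dT + gX + e1. Subtracting gives Y1 − Y0 = c + dT + (e1 − e0). The terms in b and g cancel, so with complete data d is the difference in mean change, with or without X.

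**2. Variance.** In units of the outcome variance:
- change score: 2(1−rho)
- baseline-adjusted: 1−rho²
- ratio, adjusted to change: (1+rho)/2

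**3. Power.** SE = sqrt(variance × 4/300); power = Phi(0.30/SE − 1.96); detectable difference at 80% power = (1.96 + 0.84) × SE.

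| rho | Variance, change / adjusted | Ratio | SE, change / adjusted | Power, change / adjusted | Detectable difference (SD), change / adjusted |
|---|---|---|---|---|---|
| 0.3 | 1.40 / 0.91 | 0.65 | 0.137 / 0.110 | 59% / 78% | 0.383 / 0.309 |
| 0.5 | 1.00 / 0.75 | 0.75 | 0.115 / 0.100 | 74% / 85% | 0.323 / 0.280 |
| 0.7 | 0.60 / 0.51 | 0.85 | 0.089 / 0.082 | 92% / 95% | 0.251 / 0.231 |

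An adjusted analysis of 300 × ratio = 195, 225 or 255 Veterans matches the precision of the planned test on 300.

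**4. Chance imbalance.** Suppose the arms differ by D SD at baseline and treatment has no effect. The expected follow-up difference is rho × D, so the change contrast shifts by (1−rho) × D in size. For D = 0.2 that is 0.14, 0.10 and 0.06 SD at rho 0.3, 0.5 and 0.7.

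**5. Unequal SDs.** With SDs s0 and s1, the variance difference is (s0² + s1² − 2·rho·s0·s1) − s1²(1−rho²) = (s0 − rho·s1)². This is never negative, so in large samples adjustment does not lose precision. The gain shrinks if the disability entry criterion makes s0 smaller than s1.

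**6. Numerical illustration.** One simulated data set (N = 300, rho about 0.53) shows the mechanism; it does not predict this trial's result. Interaction estimates (SE):
- change-score regression: −0.3952 (0.1071)
- mixed model with no covariates: −0.3952 (0.1071)
- with age, sex, education and baseline PHQ-8 as main effects: −0.3952 (0.1071)
- with a therapist intercept added: the same
- unstructured covariance, with or without covariates: −0.3952 (0.1068)
- ANCOVA on baseline: −0.2953 (0.0942)
- baseline means constrained equal (unstructured covariance): −0.2953 (0.0932)

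The estimate did move in these cases:
- a repeatedly measured covariate added: −0.3925 (0.1085)
- covariate-by-time terms: −0.4069 (0.1077)
- 21% of post values missing: −0.3516 (0.1204) without time-constant covariates, −0.3454 (0.1197) with them; completers' change scores gave −0.3604 (0.1213)

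**The case against.** The planned test is valid. H1 is worded as greater improvement, which is what the interaction measures, and the model also yields the within-arm contrasts. A covariate effect that is the same at both times cancels within each person, which is why its main effect is inert; only an association with change is left unaddressed. The mixed model also keeps participants who have no post value, whereas simple ANCOVA drops them. All of this stands, and it makes the point one of efficiency and chance imbalance rather than error.

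A reader might go further and infer that the planned covariates can never alter the H1 test. The documents do not support that, for three reasons.

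- The Reducing Attrition section plans to control for variables measured at the assessments. Entered as repeated values, these would move the estimate; being post-randomisation, they could also bias it.
- PHQ-8 and PCL are measured again after baseline, and the Data Analysis section does not say that only their baseline values enter, or that they enter only as main effects.
- Under intention to treat with missing post values, the model is no longer exactly the change-score comparison, and even time-constant covariates shift it slightly.

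The size of the power gain depends on assumed inputs. At rho 0.7 it is about 3 percentage points; the 19-point gain needs rho 0.3.

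**Conclusion.** The point holds as an efficiency and chance-imbalance improvement. With two time points and complete data, the H1 test is the unadjusted difference in mean change, and baseline covariates entered only as time-constant main effects do not change it. Baseline adjustment would cut the variance by 35%, 25% or 15% at rho 0.3, 0.5 or 0.7 if SDs are equal. This ratio does not depend on N, so it also applies if fewer than 300 are analysed.

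The power figures rest on all the assumptions listed and are a range, not a forecast. A reader might also infer that the planned test is biased. It is not biased under randomisation; the weakness is lower precision and sensitivity to the baseline imbalance that happens to occur.

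**What to change.** In Data Analysis (a. Data), keep the mixed model for H1 but constrain the baseline WHO-DAS means to be equal across arms, that is, no treatment main effect at baseline. The treatment effect is then the between-arm difference in the post-intervention score. State the covariance between the two times; the check above used an unstructured one for this model. The alternative is ANCOVA of the post-intervention score on baseline WHO-DAS.

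Enter age, gender, education and a pre-specified list of other baseline covariates, using baseline values only, with covariate-by-time terms (in ANCOVA, as ordinary covariates). Use the same form for H2a, H2b, H3a and H3b. The within-arm improvement contrasts can still be reported from the constrained model.

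The cost is SAP wording only, because baseline and 12-week WHO-DAS are already scheduled. The one small downside is that simple ANCOVA drops participants with no post value; the constrained mixed model avoids this and is the better choice.
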